7. RATIONALE AND BACKGROUND

COPD is a leading cause of morbidity and mortality throughout the world. Long-acting bronchodilator medications, which include long-acting β2-agonists (LABAs) and the long-acting muscarinic antagonists (LAMAs) such as tiotropium, are the central maintenance therapy to the management of COPD, with inhaled corticosteroids (ICSs) added with increasing severity. The up-to-date GOLD guideline recommends to initiate ICS/LABA in patients with high blood eosinophils level and frequent exacerbation history[P21-01394]. However, ICS containing therapy has been widely used inappropriately in real world practice.

The role of ICS in COPD has been debated for decades and studies have been conducted to investigate the effect of ICS-containing therapy in patients with COPD. INSPIRE [P07-11820] study indicated that ICS/LABA and tiotropium showed similar effects on the reduction of exacerbations, while the risk of pneumonia was higher in the ICS/LABA group. And the FLAME [P16-05628] study showed LAMA/LABA was superior to ICS/LABA in terms of exacerbation prevention, while in some newly published data focusing on FDC triple therapy showing reversed results.

With more and more fixed dose combination medications, i.e. LAMA/LABA, ICS/LABA/LAMA, approved and prescribed in recent years, it is of clinical interests to understand the effectiveness and safety profile of these therapies in real world settings.

The aim of this real world study is to assess effectiveness and safety profile between tiotropium/olodaterol (Tio/Olo) and ICS/LABA. The primary outcome of the study will be time to first moderate or severe COPD exacerbations. Other outcomes include time to ICS/LABA/LAMA escalation, rate of escalation to triple therapy, pneumonia and rescue medication use.

NIS Protocol Page 22 of 48 BI Study Number: 1237-0110 c38660249-01

Proprietary confidential information © 2022 Boehringer Ingelheim International GmbH or one or more of its affiliated

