8. RESEARCH QUESTION AND OBJECTIVES

Primary objective:

• To compare time to the first moderate or severe COPD exacerbations between initiators of Tio/Olo and ICS/LABA in a real world setting;

Secondary objectives:

- To compare time to escalation to triple therapy between initiators of Tio/Olo and ICS/LABA;
- To compare the rate of escalation to triple therapy between initiators of Tio/Olo and ICS/LABA;
- To compare the time to first hospitalization for community-acquired pneumonia between initiators of Tio/Olo and ICS/LABA;
- To compare the number of prescriptions of rescue medication between initiators of Tio/Olo and ICS/LABA;
- To compare the annualized rate of moderate or severe COPD exacerbation between initiators of Tio/Olo and ICS/LABA..

NIS Protocol Page 23 of 48 BI Study Number: 1237-0110 c38660249-01

Proprietary confidential information © 2022 Boehringer Ingelheim International GmbH or one or more of its affiliated

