9.7.1 Main analysis

All variables, including patient characteristics, baseline measures, and outcomes, will be analyzed descriptively.

- For all analyses, variables will be reported as follows: Continuous variables (e.g., age) will be presented as means (with standard deviation, SD) and/or medians (with interquartile range, IQR), minimum, maximum.
- Categorical variables (e.g., sex) will be presented as absolute and relative frequencies.

All analyses will be presented for each treatment group (Tio+Olo vs LABA/ICS) overall. We will first describe formation of the study cohort. Propensity score matching will be used to balance the baseline characteristics of patients in the two treatment groups. The covariates used to calculate the propensity score would be specified in the SEAP. All the analyses will be performed on patients after propensity score matching. Patient characteristics at baseline in patients treated with Tio+Olo and patients treated with LABA/ICS will be described separately using standard descriptive statistics after propensity score matching. Absolute standardized differences (ASDs) will be used to compare the characteristics between the two

NIS Protocol Page 30 of 48 BI Study Number: 1237-0110 c38660249-01

Proprietary confidential information © 2022 Boehringer Ingelheim International GmbH or one or more of its affiliated

groups after propensity score matching, in which a >0.1 ASD indicates a meaningful difference.

For the analysis of the primary outcome, individuals will be followed up from the index date until the first moderate or severe COPD exacerbation. The data after the earliest date of the following would be censored: 1) disenrollment; 2) the end of the study period; 3) death; 4) discontinuation of the index drug (except for switching from the index ICS/LABA to a different ICS/LABA); 5) escalation to triple therapies (ICS/LAMA/LABA free or fix dose combination). Cox proportional hazard regression model will be used to compare the time to event between the two treatment groups, while accounting for the potential baseline differences between them. Other known predictors will also be included in the model as covariates. It will provide an estimate of the hazard ratio (HR) of time to the first moderate or severe COPD exacerbation associated with Tio+Olo use relative to LABA/ICS use, along with 95% confidence intervals (CI). The analysis will be on-treatment.

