**Secondary objectives:**

- To compare time to escalation to triple therapy between initiators of Tio/Olo and ICS/LABA;
- To compare the rate of escalation to triple therapy between initiators of Tio/Olo and ICS/LABA;
- To compare the time to first hospitalization for community-acquired pneumonia between initiators of Tio/Olo and ICS/LABA;
- To compare the number of prescriptions of rescue medication between initiators of Tio/Olo and ICS/LABA
- To compare the annualized rate of moderate or severe COPD exacerbation

The study period between 1st January 2014 and 31st December 2019 apply to secondary objectives above.

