## **10. DATA ANALYSIS**

### **10.1 MAIN ANALYSIS**

All variables, including patient characteristics, baseline measures, and outcomes, will be analyzed descriptively.

- For all analyses, variables will be reported as follows: Continuous variables (e.g., age) will be presented as means (with standard deviation, SD) and/or medians (with interquartile range, IQR), minimum, maximum.

- Categorical variables (e.g., sex) will be presented as absolute and relative frequencies.

All analyses will be presented for each treatment group (Tio+Olo vs LABA/ICS) overall. We will first describe formation of the study cohort. Propensity score (PS) matching will be used to generate two comparable treatment groups. All covariates, except season of index date, will be used to estimate the propensity score with logistic regression. Patients in LABA/ICS group will be individually matched to patients in the Tio/Olo group with 1:1 ratio. A caliper of 0.06 standard deviation of logit (propensity score) will be used to define the range of estimated PS within which to select the comparator. Within that range the LABA/ICS patient with the closest estimated propensity score to the Tio/Olo patient will be selected.

Patient characteristics at baseline in patients treated with Tio+Olo and patients treated with LABA/ICS will be described separately using standard descriptive statistics after propensity score matching. Absolute standardized differences (ASDs) will be used to compare the characteristics between the two groups after propensity score matching, in which a  $>0.1$  ASD indicates a meaningful difference.

All the analyses for primary outcome and secondary outcomes will be performed on patients after propensity score matching. Baseline characteristic table shell are provided in [Table 1](#). The propensity score matching will be carried out once without re-matching.

For the analysis of the primary outcome, individuals will be followed up from the index date until the first moderate or severe COPD exacerbation. The data after the earliest date of the following event would be censored:

- 1) disenrollment
- 2) the end of the study period
- 3) death
- 4) discontinuation of index drug use (a lapse of 45 days without subsequent prescription)
- 5) switching from Tio/Olo to ICS/LABA or from ICS/LABA to Tio/Olo
- 6) escalation to triple therapies (ICS/LAMA/LABA free or fix dose combination)

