Note that per study protocol, switching from one ICS/LABA to another ICS/LABA is not a censoring event.

Univariate proportional hazard regression model will be used to compare the time to event between the two treatment groups. It will provide an estimate of the hazard ratio (HR) of time to the first moderate or severe COPD exacerbation associated with Tio+Olo use relative to LABA/ICS use, along with 95% CI. In the event that there are baseline covariates with unequal distribution between the treatment groups, defined as absolute standardized difference larger than 0.1, the covariate(s) will be included in a multiple regression model in addition to the exposure status (Tio/Olo or LABA/ICS).

The analysis of the secondary objectives related to time to triple therapy escalation and time to first hospitalization for community-acquired pneumonia will be univariate proportional hazard regression model with an as-treated approach, similar to that of the primary analysis. The estimate of hazard ratio (HR) of time to triple therapy escalation and first hospitalization for community-acquired pneumonia associated with Tio+Olo use relative to LABA/ICS use,

[figure not shown]
Proprietary confidential information © 2022 Boehringer Ingelheim International GmbH or one or more of its affiliated companies

along with 95% CI will be provided. For the analysis of these time-to-event outcomes, patients will be followed until the event of interest or earliest of the date of the follows, whichever happened first:

- 1) outcome event of interest;
- 2) disenrollment;
- 3) the end of the study period;
- 4) death;
- 5) discontinuation of index drug use (a lapse of 45 days without subsequent prescription)
- 6) switching from Tio/Olo to ICS/LABA or from ICS/LABA to Tio/Olo

In the event that there are baseline covariates with unequal distribution between the treatment groups, defined as absolute standardized difference larger than 0.1, the covariate(s) will be included in a multiple regression model in addition to the exposure status (Tio/Olo or LABA/ICS).

[figure not shown]
Proprietary confidential information © 2022 Boehringer Ingelheim International GmbH or one or more of its affiliated companies

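### The primary hazard ratio censors at escalation to triple therapy with no visible justification or test of independent censoring, and may be biased if escalation tracks exacerbation risk differently in the two arms

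*SAP*

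**What the plan says.** - SAP 10.1 censors the primary outcome at disenrollment, end of study, death, a 45-day lapse in the index drug, a switch between Tio/Olo and ICS/LABA, and "6) escalation to triple therapies (ICS/LAMA/LABA free or fix dose combination". Protocol 9.7.1 has the same escalation rule: "5) escalation to triple therapies (ICS/LAMA/LABA free or fix dose combination".
- The protocol declares the approach: "The analysis will be on-treatment".
- SAP 10.1 gives the model: "Univariate proportional hazard regression model will be used to compare the time to event between the two treatment groups". Covariates enter only if a baseline characteristic has an absolute standardised difference above 0.1 after matching. Protocol 9.7.1 differs: "Other known predictors will also be included in the model as covariates".
- Escalation is itself compared between arms, as a time ("To compare time to escalation to triple therapy between initiators of Tio/Olo and ICS/LABA", Protocol 8) and as a rate ("To compare the rate of escalation to triple therapy between initiators of Tio/Olo and ICS/LABA", SAP 5).
- Protocol 7 describes maintenance treatment "with inhaled corticosteroids (ICSs) added with increasing severity". The severity scale (Protocol 9.3.3, SAP 7.3) also grades patients partly by treatment: monotherapy is mild, LAMA plus LABA is moderate.
- The Table 2 shell holds hazard ratios only, with no counts of censoring by reason.
- A SAP section between 10.1 and 10.3 is redacted. The checklist in Protocol Annex 2 cites a section 9.7.2 that is not in the visible text.

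**The concern.** A Cox model that censors at escalation needs one condition, whether or not the plan states it. At any time, patients removed by escalation must have the same exacerbation hazard as patients in the same arm who remain, given what the model conditions on. Here that is baseline information only. If prescribers add a third drug because a patient is getting worse, high-risk person-time leaves the risk set. Matching at the index date cannot repair this, because the worsening comes later.

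The arms also escalate by different steps: an ICS is added to Tio/Olo, a LAMA to ICS/LABA (Protocol 9.2.2). The link between escalation and risk could therefore differ by arm even if the rates are the same.

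At stake is the reading of the primary HR. If escalation removes more high-risk time from ICS/LABA, a Tio/Olo benefit is understated. If it removes more from Tio/Olo, the benefit is overstated.

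**Working it through.** **Inputs from the documents (Protocol 9.5).** Comparator: 25% with a first event by 103 days. Design HR 0.9, two-sided alpha 0.05, power 90%, 6 years, 4978 patients, 1:1.

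- Comparator hazard: −ln(0.75)/103 = 0.002793 per day, or 1.020 per year.
- Design effect: ln(0.9) = −0.105.
- Events required (Schoenfeld): 4 × (1.960 + 1.282)² / 0.105² ≈ 3787. The standard error of the log HR is then 2/√3787 = 0.0325.
- The plan's own 4978 is not reproduced exactly. Uniform entry over 6 years gives 4574, and 4978/4574 = 1.088. An unstated loss of about 8% (4574/4978 = 0.919) would bridge the gap, so 4978 is not shown to be wrong and is not part of this point.

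**Assumptions, since the plan gives no escalation rate.** Two simulation models were used, each with 1,000,000 patients per scenario and uniform entry over 6 years. The HR with censoring at escalation is divided by the HR in the same patients without it.

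*Model A, lasting differences in risk.* Hazard = λ × Z × HR, where Z is a gamma frailty with variance 0, 0.5 or 1, and λ is set to give 25% at 103 days. Discontinuation is 1 per year. Escalation averages 0.15 to 0.6 per year and is either unrelated to Z or proportional to Z. The ranges below cover true HRs of 0.9 and 1.0.

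| Escalation process | HR ratio, Tio/Olo higher | HR ratio, ICS/LABA higher |
|---|---|---|
| Unrelated to risk, four-fold rate difference | 0.997 to 1.001 | 0.996 to 1.001 |
| Tracks risk equally, equal rates | 0.996 to 1.001 | same |
| Tracks risk, two-fold rate difference | 0.967 to 0.979 | 1.019 to 1.029 |
| Tracks risk, four-fold rate difference | 0.915 to 0.942 | 1.056 to 1.087 |
| Equal rates, tracks risk in that arm only | 0.938 to 0.960 | 1.040 to 1.060 |

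In the largest case (frailty variance 1, four-fold, conditional HR 0.9) the HR goes from 0.925 to 0.847 if Tio/Olo escalates more (17.0% v 4.8% escalated). It goes from 0.926 to 1.003 if ICS/LABA does (5.1% v 16.2%).

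With a true HR of 1.0, the chance of a significant result follows from z = |ln ratio| / (2/√events), with events = 4978 × the simulated event fraction:
- ratio 0.979: 4978 × 0.390 = 1941 events, z = 0.47, rejection about 7.5%;
- ratio 0.942: 4978 × 0.370 = 1842 events, z = 1.28, about 25%;
- ratio 0.921: 4978 × 0.349 = 1737 events, z = 1.72, about 40%.

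*Model B, worsening after the index date.* Worsening occurs at 0.5 per year and multiplies the hazard by 1.5 to 3. Escalation occurs only from the worsened state, at 0.5 to 2 per year. Other stopping is 0 or 1 per year. The shift in log HR, as a share of 0.105, is:
- equal rates: 0 to 3%;
- Tio/Olo 1 v ICS/LABA 2: 9 to 25%;
- 0.5 v 2: 15 to 45%;
- 2 v 1: 9 to 34%, in favour of Tio/Olo.

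On the HR scale, 9% is 0.09 × 0.105 = 0.009 (about 1%), and 45% is 0.45 × 0.105 = 0.047 (about 5%).

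*Would weights help?* In Model B, with the hazard doubled on worsening and other stopping at 1 per year, HRs without escalation censoring, with it, and with it plus weights were:
- 0.909, 0.922, 0.909 (1 v 2);
- 0.910, 0.934, 0.912 (0.5 v 2);
- 0.899, 0.884, 0.901 (2 v 1).

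The weights used the true worsening time and censoring rate, so this is a best case.

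**The case against.** A reader might infer that the HR is biased whenever the arms escalate at different rates. The documents do not support that, and the first and last rows of the table refute it: a four-fold difference unrelated to risk leaves the HR unchanged, while equal rates with unequal dependence move it. A reader might also infer that the plan contradicts itself by linking ICS to severity. Protocol 7 is general background on ICS. It does not cover adding a LAMA, and it also says that ICS are often used inappropriately, which points to a looser link with risk. Making escalation a secondary outcome does not say that the arms will differ.

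Other points stand in part:
- On-treatment analysis is a deliberate choice. That settles the question asked, but not whether censoring is independent.
- Escalation prompted by a first post-index exacerbation comes after the primary event and does no harm here.
- Model B allows escalation only after worsening, which maximises dependence. At its milder settings (two-fold rates, hazard multiplied by 1.5 to 2, other stopping 1 per year) the shift is 0.010 to 0.015 in log HR, under half of 0.0325.
- SAP 7.2.2 dates escalation at day 30 of triple therapy. If that date also governs censoring, the shift fell by roughly a fifth in test runs.
- The protocol's covariate-adjusted model would remove the part of the dependence that baseline predictors explain, but not the part arising after the index date.
- The redacted SAP 10.2 may hold a sensitivity analysis, so it cannot be said that none exists.

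**Conclusion.** The point holds in conditional form. The primary HR may be biased if pre-exacerbation escalation depends on exacerbation risk and its rate, or its strength of dependence, differs between arms. The visible plan neither argues for independent censoring nor checks it.

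Direction and size are unknown. With risk-dependent escalation and two-fold to four-fold rate differences, the shift is about 1% to 9% of the HR in either direction. It is close to zero when rates and dependence are equal. These figures rest on assumed escalation, worsening, frailty and discontinuation values, none of which comes from the documents. Against a design HR of 0.9, the upper part of that range matters. The simulations concern escalation only. They treat other stopping as uninformative, so they give no evidence of bias from switch or lapse.

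**What to change.** In SAP 10.1 and Table 2:

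1. Keep the on-treatment HR as the primary result.
2. Add the numbers censored, by reason and arm. This alone shows whether the concern is live.
3. Report beside the primary HR a sensitivity HR with inverse-probability-of-censoring weights for escalation, extended to switch and lapse if their counts differ by arm. Estimate the weights by arm from baseline covariates and time-updated claims: reliever dispensings, other respiratory drugs, visits and admissions.
4. If the weighted and unweighted HRs differ materially, state this as a limitation on the primary conclusion. Do not make agreement a condition for concluding.
5. Optionally show an HR by initial treatment that does not censor at lapse, switch or escalation, labelled as answering a different question and diluted by later treatment changes.
6. Reconcile the protocol's covariate-adjusted Cox model with the SAP's univariate one.
7. If redacted section 10.2 already holds such an analysis, report it beside the primary HR.

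Cost: SAP wording and some programming on claims already held, with no new patients or data. The weighted HR will have a somewhat wider interval. It corrects only for worsening visible in claims, which lack spirometry and smoking (SAP 6.1).

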### **(1). Time to triple therapy escalation after index date**

Triple therapy escalation, defined as any LAMA/LABA/ICS fixed dose combination or any concurrent use for 30 consecutive days of the following:

- a. any LAMA/LABA fixed dose combination + any ICS single formulation
- b. any LAMA single formulation + any LABA/ICS fixed dose combination
- c. any LAMA single formulation + any LABA single formulation + any ICS single formulation

The event date will be the 30th day after initiation of triple therapy.

As time-to-event data, the analysis will be univariate proportional hazard regression analysis to estimate the hazard ratio (Tio/Olo vs. comparator) and its 95% CI.

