### **(2). Incidence rate of triple therapy initiation (first event per patient)**

Triple therapy escalation, defined as any LAMA/LABA/ICS fixed dose combination or any concurrent use for 30 consecutive days of the following:

- a. any LAMA/LABA fixed dose combination + any ICS single formulation
- b. any LAMA single formulation + any LABA/ICS fixed dose combination
- c. any LAMA single formulation + any LABA single formulation + any ICS single formulation

For incidence rates, it will be calculated for each cohort as follows:

Incidence rate among the Tio+Olo cohort = (total number of patients in the Tio+Olo cohort experiencing an event of interest for the first time during the given time period) / (total person-time at risk from current use of Tio+Olo during the given period)

Incidence rate among the comparison cohort = (total number of patients in the comparator LABA/ICS cohort experiencing an event of interest for the first time during the given time period) / (total person-time at risk from current use of comparator LABA/ICS during the given period)

The incidence rate ratio (IRR) and incidence difference for the outcome in the Tio+Olo - exposed group relative to that in the comparator group will be derived as follows:

Incidence rate ratio = incidence rate from the Tio+Olo cohort divided by the incidence rate from the matched comparator cohort.

Incidence difference = incidence rate from the Tio+Olo cohort – incidence rate from the matched comparator cohort

The IRR and their 95% CIs will be calculated using univariate negative binomial model. Incidence differences and their 95% confidence intervals will also be derived.

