## Appendix 1. SAS code template for negative binomial model in the analysis of the secondary outcomes of interest

The following codes are provided by Boehringer Ingelheim statistician

```
PROC GENMOD DATA=test;
CLASS treat (ref='LABA/ICS') cova_cat;
MODEL ep_count = treat cova_cat cova_con /
DIST=negbin LINK=LOGTYPE3 OFFSET=logt;
LSMEANS treat / DIFF CL;
ESTIMATE 'Treatment effect on ratio-scale' treat 1 -1 / EXP;
RUN;
```

(In the model,  
treat: Tio+Olo group OR LABA/ICS group;  
Cova\_cat: categorical covariates;  
Cova\_con: continuous covariates)

For univariate analysis, Cova\_cat and Cova\_con are not applicable.

For calculating incidence rate ratio with 95% CI of triple therapy initiation (Tio+Olo vs. LABA/ICS),  
ep\_count (response): 1 (triple therapy initiation occurred per patient) or 0 (triple therapy initiation not occurred per patient);  
logt: nature log of the time at risk (first event per patient)

For calculating ratio (with 95% CI) of annualized rate of moderate or severe COPD exacerbations and annualized rate of prescriptions of rescue medications (Tio+Olo vs. LABA/ICS),  
ep\_count (response): number of events per patient  
logt: nature log of the time at risk per patient

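### For time to triple therapy escalation, the switch item in SAP 10.1 can censor a replacement-route escalation at day 0, before its day-30 event date, and no visible text gives precedence.

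*SAP*

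**What the plan says.** SAP 10.1 gives one follow-up list for time to triple escalation and time to first pneumonia hospitalization: "patients will be followed until the event of interest or earliest of the date of the follows, whichever happened first". Besides the event, disenrollment, end of study, death and a 45-day lapse, it lists "6) switching from Tio/Olo to ICS/LABA or from ICS/LABA to Tio/Olo". The visible SAP does not define a switch.

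SAP 7.2.2 (1) counts a fixed triple inhaler as escalation. It also counts 30 consecutive days of concurrent use of one of three free combinations:

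- (a) "any LAMA/LABA fixed dose combination + any ICS single formulation"
- (b) "any LAMA single formulation + any LABA/ICS fixed dose combination"
- (c) three single inhalers, one from each class.

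The event date is the 30th "day after initiation of triple therapy".

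SAP 7.2.2 (2), "Incidence rate of triple therapy initiation (first event per patient)", uses the same definition without an event date or a switch rule. Its person-time is that from current use of the index treatment. The code template in SAP Appendix 1 adds only "logt: nature log of the time at risk (first event per patient)".

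Protocol 9.7.1 has no item for a switch between arms in its list for these outcomes; the SAP added it. The protocol does list discontinuation of the index drug, with an exception only for a change between ICS/LABA products.

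**The concern.** Routes (a) and (b) can each be reached in two ways. The patient may keep the index inhaler and add the missing component, or may replace the index inhaler with the other arm's inhaler plus a single agent. In the second case the same change of prescription begins triple therapy and is also a move between Tio/Olo and ICS/LABA. The switch is dated on the day it happens and the event 30 days later, so an earliest-date rule keeps the censoring and discards the event.

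The follow-up rule would then remove events that the outcome definition includes. Two competent programmers could produce different event counts from the same data. If the loss differs between arms, the hazard ratio and the incidence rate ratio are distorted. If it is equal, the ratios hold but both reported incidence rates are too low. A choice of precedence made after seeing the data would be a post-hoc choice on a comparative result.

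**Working it through.** **Plan figure.** There is none to reproduce. The documents state no event rate, size or power for triple escalation. The 2489 per arm in Protocol 9.5 was derived for the primary outcome and serves below only to give a scale.

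**Date order** (day 0 = change of prescription)

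| Change | Switch item met | Event date | Result, read literally |
|---|---|---|---|
| Tio/Olo kept, ICS added | no | day 30 | event |
| ICS/LABA kept, LAMA added | no | day 30 | event |
| Tio/Olo replaced by LAMA + ICS/LABA | day 0 | day 30 | censored, event lost |
| ICS/LABA replaced by Tio/Olo + ICS | day 0 | day 30 | censored, event lost |

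For the primary outcome SAP 10.1 lists both switching and escalation, but both censor, so an overlap removes no outcome event. For the escalation outcome one is the event and the other pre-empts it.

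**Effect on the hazard ratio.** Let sT and sC be the shares of escalations by the replacement route on Tio/Olo and ICS/LABA. Only the remaining fraction is observed in each arm, so

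observed HR ≈ true HR × (1 - sT)/(1 - sC).

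Assumptions for the simulation check: triple-therapy starts at 0.2 per year in both arms (true HR 1), event 30 days later, other censoring at the earlier of an exponential time with median 6 months and a uniform time over 0 to 6 years.

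| sT / sC (assumed) | Formula | Simulated HR |
|---|---|---|
| 10% / 5% | 0.90/0.95 = 0.95 | 0.95 |
| 25% / 5% | 0.75/0.95 = 0.79 | 0.80 |
| 25% / 25% | 1.00 | 1.00, within simulation error |
| 10% / 25% | 0.90/0.75 = 1.20 | 1.21 |
| 5% / 25% | 0.95/0.75 = 1.27 | 1.27 |

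At 25%/25% both rates fall from about 0.17 to 0.13 per person-year. If sC is 5%, a 10% shift in the HR needs sT = 1 - 0.9 × 0.95 = 14.5%.

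**Against sampling error.** With 2489 per arm and 0.2 per year, about 246 escalations per arm are expected before any loss.

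- 25%/5%: 246 × 0.75 = 184.5 and 246 × 0.95 = 233.7 events remain. SE of log HR = √(1/184.5 + 1/233.7) = 0.098. |ln 0.789| = 0.236, or 2.4 SE.
- 10%/5%: 221.4 and 233.7 remain. SE = 0.094. |ln 0.947| = 0.054, or 0.5 to 0.6 SE.
- At 0.1 or 0.3 per year (132 or 354 escalations per arm before loss) the 25%/5% shift is 1.8 or 2.9 SE, and the 10%/5% shift 0.4 or 0.7 SE.

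**Check of the remedy.** If confirmed escalations are kept to day 30, the simulated HR is 0.99 to 1.01 with few or no unconfirmed replacement starts. With unconfirmed starts at 0.4 per year in one arm and 0.1 in the other, censored back at the switch, it is 0.98 to 1.03. The size agrees with exp((0.4 - 0.1) × 30/365) = 1.025.

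**The case against.** The best defence is the as-treated design. The analysis is described as "with an as-treated approach, similar to that of the primary analysis", and the incidence-rate person-time is that from current use of the index treatment. A patient who has left the index inhaler is no longer in current use at day 30, so ending follow-up at the switch could be intended. That does not fit the outcome definition: a fixed triple inhaler and three single inhalers both require the index inhaler to be dropped, yet SAP 7.2.2 (1) counts them. Escalation by replacement is therefore within the intended outcome. What stands is that the fix must say how the person-time changes.

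Second, a switch is undefined, and an analyst could treat any start of triple therapy as escalation rather than a switch. The primary list names the two separately, and Protocol 9.2.2, for the primary outcome, describes adding a component to the index inhaler. On that reading nothing is lost. But no visible text makes the two exclusive or gives one precedence for the escalation outcome, so the ambiguity remains.

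Third, the size is assumed. This stands in full.

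A reader might also infer that the pneumonia analysis is wrong because the shared list omits the escalation censoring used for the primary. The documents do not support that. Protocol 9.7.1 and SAP 10.1 agree on the pneumonia list, the rescue-medication list in SAP 10.1 omits escalation too, and neither choice is always closer to the truth. A supplementary analysis could also sit in the redacted SAP sections.

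**Conclusion.** The concern holds for the triple-escalation outcomes. Read literally, SAP 10.1 discards escalations in which the index inhaler is replaced by the other arm's inhaler, although SAP 7.2.2 (1) counts them. The date order follows from the visible text alone. The size depends on route shares, which the documents do not give: it is about half a standard error at 10%/5% and about 2.4 at 25%/5%, assuming 0.2 escalations per year and 2489 per arm.

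A reader might infer that the loss favours Tio/Olo, because SAP Appendix 3 lists five ICS/LABA products that trigger the item from Tio/Olo, while only one of three LAMA/LABA products triggers it from ICS/LABA. Product counts are not shares of escalations. They mean that equal losses cannot be presumed, but they do not settle the direction.

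The primary outcome is not affected by this loss. Some SAP sections are redacted, so the conclusion is limited to the visible text.

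Side note: the start of the 45-day lapse is not stated. Assuming a 30-day supply and a change at refill, a move to a fixed triple inhaler has its event on day 60 after the last index dispensing. That event is lost if the lapse runs from dispensing (day 45) and kept if it runs from end of supply (day 75).

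**What to change.** For the triple-escalation outcomes, add to SAP 10.1:

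- A change of inhaler that starts a regimen meeting SAP 7.2.2 (1) is not a switch or a discontinuation while the 30-day criterion is assessed.
- A confirmed escalation takes precedence. If it is not confirmed, the patient is censored at the date of the switch or lapse.
- The same rule and event date apply to the incidence rate in SAP 7.2.2 (2) and the Appendix 1 offset, and person-time from current use then includes the confirmation window of up to 30 days.
- The number of patients affected by the rule is reported by arm.

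It would help to state in the same place when the 45-day lapse starts.

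The cost is a few lines of SAP text and programming. The rule uses later information, because confirmation is known only at day 30; this moved the HR by about 2 to 3% in the unfavourable case simulated and should be noted in the SAP. Protocol 9.7.1 has no cross-arm switch item for these outcomes, so that part conflicts with nothing there; the new text should be read against its discontinuation item.
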